7.2 METHODS FOR ASSESSING, RECORDING, AND ANALYZING EFFICACY

See detailed study procedures section 4.5 and statistics section 9.

8.1 SAFETY PARAMETERS

The following safety parameters will be monitored and evaluated:

- Ocular physiology characteristics
- Lens fitting characteristics
- Adverse events
- Ocular symptoms
- Snellen distance visual acuity
- Reasons for discontinuation
- Reasons for unplanned lens replacement
- Product Quality Complaints

Safety parameters will be tabulated using frequency distribution tables and descriptive statistics. Adverse events will be listed by subject/eye. There will be separate summary tables for adverse events and infiltrative adverse events. Statistical methods for analyzing safety data, if any, are provided in section 9.

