1.8 PROTOCOL SYNOPSIS

| |
|---|
| Protocol Number and Title: CR-5903 Evaluation of a Novel Toric Multifocal Contact Lens in Hyperopic Presbyopes |
| Sponsor: JJVC, [name] |
| Investigational Products: Investigational Toric Multifocal Contact Lens for Presbyopia |
| Ancillary Supplies: ETDRS Light Box, Near Guillon-Poling Charts, Near Lamps, Guillon-Poling Chart Holder, Pupillometer, Rewetting drops, saline solution for final lens storage, and lens cases. |
| Randomization and Dispensing: Single Arm,(Non- Randomized) Dispensing trial |
| Microbiology or Other Testing Laboratory: Not Applicable |
| Phase or Type of Study: Feasibility |

Primary Objective: To evaluate the subjective feedback of a multifocal contact lens in a population of presbyopes with hyperopia.

Secondary Objectives:

- 1 – Evaluate the fit of the toric multifocal lens.
- 2 – Evaluate the ocular physiological response of the toric multifocal lens.

Study Design: This is a single-masked, single-arm, dispensing feasibility study. There will be three study visits. Visit 1 will include baseline measurements and screening to ensure eligibility. Eligible subjects will be fit in study lenses and dispensed for 6-8 days. At Visit 2 additional measurements will be performed and it will be determined if lens optimization is required and lenses dispensed for an additional 6-8 days. At Visit 3 the primary endpoint data used for analysis will be collected. The lenses will be worn as a daily disposable.

Sample Size: A total of approximately 60 eligible subjects will be enrolled into the study with 48 subjects targeted to complete. An attempt will be made to evenly distribute the subjects across the following ADD groups and ATR & WTR.

Distribution of the 48 Completed Hyperopes will be 24 ATR and 24 WTR

| +0.75 to +1.50 ADD | | +1.75 to +2.50 ADD | |
|-----------------------|-----|--------------------|-----|
| ATR | WTR | ATR | WTR |
| ≈12 | ≈12 | ≈12 | ≈12 |

Screening: Healthy male and female volunteers (from 40 to 70 years of age) with a need for presbyopic correction in both eyes will be screened as per criteria outlined below.

Qualification, Dispensing and Follow-Up Procedures:

Screening: Subjects will complete informed consent. Demographics and medical history will be reviewed and baseline measurements completed. Subjects must meet all of the study inclusion criteria to continue in the study.

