4.3 EXCLUSION CRITERIA

Potential subjects who meet any of the following criteria will be excluded from participating in the study:

1. Ocular or systemic allergies or disease, or use of medication which might interfere with contact lens wear.
2. Pregnancy or lactation.
3. Currently diagnosed with diabetes.
4. Infectious diseases (e.g. hepatitis, tuberculosis) or an immune-suppressive disease (e.g. HIV).
5. Clinically significant (grade 3 or 4) corneal edema, corneal vascularization, corneal staining, tarsal abnormalities or bulbar injection, or any other corneal or ocular abnormalities which would contraindicate contact lens wear.
6. Entropion, ectropion, extrusions, chalazia, recurrent styes, dry eye, glaucoma, history of recurrent corneal erosions.
7. Any previous, or planned, ocular or intraocular surgery (e.g. radial keratotomy, PRK, LASIK, lid procedures, cataract surgery, retinal surgery, etc.).
8. A history of amblyopia, strabismus or binocular vision abnormality.
9. Any ocular infection or inflammation.
10. Any ocular abnormality that may interfere with contact lens wear.
11. Use of any ocular medication, with the exception of rewetting drops.
12. History of herpetic keratitis.
13. Participation in any contact lens or lens care product clinical trial within 30 days prior to study enrollment.

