8.3 ADVERSE EVENT DEFINITIONS

Adverse Event (AE) – An AE is any untoward (unwanted) medical occurrence in a patient or clinical investigation subject administered a test article whether or not caused by the test article or treatment. An AE can therefore be any unfavorable or unintended sign (including an abnormal finding), symptom, or disease temporally associated with the use of the test article whether or not related to the test article.

An AE includes any condition (including a pre-existing condition) that: 1) was not present prior to study treatment, but appeared or reappeared following initiation of study treatment; or 2) was present prior to study treatment, but worsened during study treatment. This would include any condition resulting from concomitant illnesses, reactions to concomitant medications, or progression of disease states. Pregnancy should be documented as an adverse event and should be reported to the clinical monitor and to the Sponsor immediately upon learning of the event

Serious Adverse Event (SAE) – An SAE is any untoward medical occurrence that:

- Results in death
- Is life threatening
- Requires in-patient hospitalization or prolongation of existing hospitalization
- Results in persistent or significant disability/incapacity (i.e., a significant persistent or permanent change, impairment, damage, or disruption to the subject's body)
- Is a congenital anomaly/birth defect, or
- Requires intervention to prevent permanent damage (the use of the investigational product resulting in a condition which requires medical or surgical intervention to preclude permanent impairment of the body structure or a body function). Important medical events that may not result in death, be life-threatening, or require hospitalization may be considered an SAE when, based upon appropriate medical judgment, they may jeopardize the patient or subject and may require medical or surgical intervention to prevent one of the outcomes listed in the above definition.

Diagnoses and conditions that are considered Serious Adverse Events include:

- Microbial Keratitis (MK)
- Iritis
- Permanent decrease in best spectacle corrected visual acuity equivalent to 2 acuity lines or greater
- Central Corneal Opacity
- Central Corneal Neovascularization
- Uveitis
- Endophthalmitis
- Hypopyon
- Hyphemia
- Penetration of Bowman's Membrane
- Persistent Epithelial Defect
- Limbal cell Damage leading to Conjunctivalization

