9.1 STATISTICAL METHODS TO BE EMPLOYED

All data summaries and statistical analyses will be performed using the SAS software Version 9.4 (SAS Institute, Cary, NC). Throughout the analysis of data, the results for each subject/eye will be used when available for summarization and statistical analysis. Unscheduled visits will be summarized separately and will be excluded from the statistical analysis.

Summary tables (Descriptive statistics and/or frequency tables) will be provided for all baseline variables, efficacy variables and safety variables as appropriate. Continuous variables will be summarized with descriptive statistics (n, mean, standard deviation (SD), median, minimum and maximum). Frequency count and percentage of subjects or eyes within each category will be provided for categorical data.

Summaries will be presented by study lens type and will be performed separately by completion status (Completed or Non Completed). All analyses will be conducted on all subjects who completed the study (see section 9.7).

Primary Endpoint:

Overall quality of vision scores will be analyzed using a linear mixed model. The model will include the experimental design factors: time point (baseline/follow-up) as fixed effects. Other baseline characteristics known of importance such as age, gender, and/or add power will be included as fixed covariates when appropriate. Site will be included as random covariates when appropriate. The covariance between residual errors from the same subject across time points will be selected based on the finite-sample corrected Akaike's Information Criterion (Keselman et al. 1998). Covariance structures considered may include: Homogenous compound symmetry (CS) and Unstructured covariance structure (UN). The structure that returns the lowest Akaike Information Criteria Corrected (AICC) will be selected as the structure that best fit the data.

Comparisons between the time points will be carried out using 95% confidence intervals constructed of least-square means (LSM) differences (follow-up minus baseline) from the linear mixed model. The non-inferiority of the

test lens relative to the control will be concluded if the lower confidence limit of LSM difference is above the non-inferiority margin -5. The superiority will be established if the lower confidence limit is above 0.

In all models, the Kenward and Roger method (Kenward and Roger, 1997) will be used for the calculation of the denominator of degrees of freedom.

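### Slit-lamp findings get no per-eye comparison with baseline, so in this single-arm study worsening within grades 0 to 2 can be offset by improvement in other eyes and not show in the tables

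*Combined protocol and SAP*

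**What the plan says.** - Safety summaries, section 8.1: "Safety parameters will be tabulated using frequency distribution tables and descriptive statistics". The same section lists adverse events by subject and eye, gives them their own summary tables, and refers to section 9 for any further methods.
- Section 9.1: "Summary tables (Descriptive statistics and/or frequency tables) will be provided for all baseline variables, efficacy variables and safety variables as appropriate". For graded findings: "Frequency count and percentage of subjects or eyes within each category will be provided for categorical data". Summaries are split by completion status. On visits outside the schedule: "Unscheduled visits will be summarized separately and will be excluded from the statistical analysis".
- Objective served, section 1.8, secondary objective 2: "Evaluate the ocular physiological response of the toric multifocal lens". Section 4.1, although its title covers secondary endpoints, defines none, so sections 8.1 and 9.1 hold the whole analysis for this objective.
- Entry limit, section 4.3: "Clinically significant (grade 3 or 4) corneal edema, corneal vascularization, corneal staining, tarsal abnormalities or bulbar injection" are excluded, along with other abnormalities that would contraindicate lens wear. Section 4.2 requires best-corrected acuity of 20/20-3 or better in each eye.
- Data collected, section 4.7.1: slit-lamp grading of each eye at Visits 1, 2 and 3 (redness in 0.5 steps, staining in 1.0 steps), and best-corrected distance acuity to the nearest letter at Visit 1 and at the Final Evaluation.
- Acuity: the safety parameter named in section 8.1 is "Snellen distance visual acuity". Section 8.3 defines harm on best spectacle-corrected acuity, for example "Permanent decrease in best spectacle corrected visual acuity equivalent to 2 acuity lines or greater".

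**The concern.** The study has no control arm. For secondary objective 2 the only available contrast is each eye with the study lens against the same eye at Visit 1, when subjects arrive wearing their habitual lenses. Section 9.1 plans such a contrast (follow-up minus baseline) for the primary vision score but for no safety measure.

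A table of grades at each visit shows how many eyes are at each grade. It does not show which eyes moved. Because current lens wearers with grade 1 or 2 signs may enter, some eyes can improve after leaving the habitual lens while others worsen on the study lens, and the table shows only the net result. A mean grade has the same weakness. The split by completion status and the separate handling of unscheduled visits mean that an eye's highest grade may sit in a different table from its baseline grade.

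What is at stake is whether the report can answer secondary objective 2 for mild to moderate signs. The primary hypothesis is not affected.

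**Working it through.** The plan states no figure on this point, so there is none to reproduce. The check asks what the planned tables can and cannot reveal.

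**Inputs.** N = 48 completers × 2 eyes = 96 eyes (sections 2.6 and 9.2). Grade 3 and 4 of the listed signs are excluded at entry (4.3). The acuity entry limit is 20/20-3 (4.2). The share of eyes at grade 2 on entry is not given, so 5% to 30% is assumed below.

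**1. Bound for grades 0 to 2.** Suppose b of N eyes are at grade 2 at both visits and the rest are at grade 0. If k eyes leave grade 2 for grade 0, k others must arrive from grade 0 for the tables to match. Any k from 0 to min(b, N − b) fits.

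| Assumed share at grade 2, both visits | b of 96 | Eyes newly at grade 2 that fit identical tables |
|---|---|---|
| 5% | 5 | 0 to 5 |
| 10% | 10 | 0 to 10 |
| 20% | 19 | 0 to 19 |
| 30% | 29 | 0 to 29 |

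**2. Worked example.** Take 76 eyes at grade 0 and 20 at grade 2. Ten eyes go from 0 to 2 and ten go from 2 to 0. At both visits:
- the counts are 76 and 20;
- the mean is (20 × 2)/96 = 0.417;
- the SD is √[(20 × 4 − 96 × 0.4167²)/95] = √(63.33/95) = 0.816;
- the median is 0.

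Every planned summary is the same at both visits. A shift table would show ten eyes worse by two grades and ten better by two.

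**3. Grade 3 or higher.** No eligible eye starts at grade 3 or 4 of an excluded sign, so b = 0 there at baseline. The count after fitting is then the count of new cases, and nothing can cancel.

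**4. Best-corrected acuity.** Assume five-letter lines at 0.02 logMAR per letter. The entry limit is 3 × 0.02 = 0.06 logMAR, and two lines are 0.20.
- A two-line loss stays inside the entry range only if the eye started at 0.06 − 0.20 = −0.14 or better, that is 20 × 10^(−0.14) = 14.5, or about 20/14.5.
- From 20/20 the eye ends at 0.20, about 20/32. From 20/20-3 it ends at 0.26, about 20/36. No eligible eye was in either category at baseline, so a fine-grained frequency table would show the loss.
- A mean can still hide it. If 10 of 96 eyes lose two lines, an average gain of 10 × 0.20/86 = 0.023 logMAR, or 0.023/0.02 ≈ 1.2 letters, in the other 86 leaves the mean unchanged.

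**The case against.** The strongest reply is that the adverse event route already works per eye. Section 8.3 counts an abnormal sign, or the worsening of an existing condition, as an adverse event. Section 8.4 requires deterioration of a baseline condition to be reported, and has the investigator and medical monitor categorise events together. Section 8.1 then lists events by subject and eye. This stands for worsening that is recognised as an event. It does not close the gap, because the only slit-lamp grade threshold in the section 8.3 definitions is grade 3 or higher. Whether a rise such as 0 to 2 is recorded rests on the judgement of an investigator who is not masked (section 4.5). The redness, staining and biomicroscopy appendices are largely redacted, so whether they give a rule cannot be judged.

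A second reply is that this is a feasibility study, that section 9.1 allows summaries as appropriate, and that shift tables are often settled at table-shell stage. It is true that nothing forbids change scores. But nothing plans them either, and they are the only contrast that addresses a stated objective.

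A third reply concerns the remedy. Comparing one baseline reading with the worst of several later ones inflates apparent worsening. If there is no true change and the readings are exchangeable and untied (an assumption), the worst of two later readings exceeds baseline with probability 2/3, against 1/2 for a single later reading. With no control arm this excess cannot be separated from harm. The objection stands, and the fix allows for it.

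A reader might also infer that unscheduled-visit findings are lost. They are not: section 6.3 requires slit-lamp findings at those visits, and section 9.1 summarises them, though apart from the scheduled data.

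**Conclusion.** The concern holds for slit-lamp signs within grades 0 to 2. The planned tables and summary statistics can be identical at Visit 1 and Visit 3 while individual eyes worsen. At an assumed 20% prevalence of grade 2, identical tables fit 0 to 19 of 96 eyes newly at grade 2; across 5% to 30%, the upper limit runs from 5 to 29. These are algebraic bounds on assumed prevalences. The upper limit needs every eye at grade 2 to improve while the same number of others worsen.

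Three stronger readings are tempting, and the documents do not support them:
- That serious new corneal findings could cancel out. New grade 3 or higher findings of the excluded signs cannot, because no eligible eye starts there.
- That a two-line loss of best-corrected acuity would go unseen. Most such losses leave the entry range. The gap is mainly in means and in eyes starting at about 20/14.5 or better. Section 8.1 also does not name best-corrected acuity, although section 8.3 defines harm by it.
- That a sizeable share of eyes will worsen unnoticed. The documents contain nothing from which to predict that share.

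The change is worth making: it improves the answer to a stated objective using data that are largely already collected.

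**What to change.** In sections 8.1 and 9.1, keep the by-visit tables and add the following for all eyes fitted with a study lens, completers or not, stating the number with a post-fit reading:

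1. For each slit-lamp sign, a per-eye shift table of Visit 1 grade by Visit 3 (or last available) grade.
2. Separately, a shift table of Visit 1 grade by worst post-fit grade, with unscheduled visits included, and a footnote that taking the maximum of several readings biases it upward.
3. In both, the number and percentage of eyes and of subjects that worsen, and that improve, by at least 1 grade (for redness, by at least 0.5 and at least 1.0).
4. Per-eye change in best-corrected acuity from Visit 1 to the Final Evaluation, in letters or lines, with eyes that meet the section 8.3 acuity-loss thresholds reconciled against the adverse event listing.

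The cutpoints are for reporting only and change no clinical rule. The cost is some wording and a few more table programs, with no added visits or procedures. The downside is that more eyes will be shown as changed; counting improvement beside worsening, and giving the Visit 3 table beside the worst-grade table, lets a reader weigh that.

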8.2 ADVERSE EVENTS

Non-Serious Adverse Events:

All non-serious adverse events, including non-serious adverse device effects, will be reported to the sponsor by the Investigator no later than 2 days from discovery for review by the Medical Monitor.

Serious Adverse Events:

The Investigator will inform the sponsor of all serious adverse events occurring during the study period as soon as possible by e-mail, fax, or telephone, but no later than 24 hours following discovery of the event. The investigator is obligated to pursue and obtain information requested by the Sponsor in addition to that information reported on the CRF. All subjects experiencing a serious adverse event must be followed up and all outcomes must be reported.

When medically necessary, the investigator may break the randomization code to determine the identity of the treatment that the subject received. The Sponsor and study monitor should be notified prior to unmasking the test articles.

In the event of a serious adverse event, the investigator must:

- Notify the Sponsor immediately
- Obtain and maintain in the subject's file all pertinent medical records, information and medical judgment for colleagues who assisted in the treatment and follow-up of the subject
- Provide the Sponsor with a complete case history which includes a statement as to whether the event was or was not related to the use of the investigational test article
- Notify the IRB/IEC as required by the IRB/IEC reporting procedure according to national regulations

Unanticipated (Serious) Adverse Device Effect (UADE):

In the event of an Unanticipated (Serious) Adverse Device Effect (UADE), the Investigator will submit a report of the UADE to the Sponsor and IRB/IEC as soon as possible, but no later than 24 hours after the Investigator first learns of the effect. This report is in addition to the immediate notification mentioned above.

The Sponsor must conduct an evaluation of the UADE and must report the results of the evaluation to FDA, the IRB/IEC and participating investigators within 10 working days after the Sponsor first receives notification of the effect.

8.3 ADVERSE EVENT DEFINITIONS

Adverse Event (AE) – An AE is any untoward (unwanted) medical occurrence in a patient or clinical investigation subject administered a test article whether or not caused by the test article or treatment. An AE can therefore be any unfavorable or unintended sign (including an abnormal finding), symptom, or disease temporally associated with the use of the test article whether or not related to the test article.

An AE includes any condition (including a pre-existing condition) that: 1) was not present prior to study treatment, but appeared or reappeared following initiation of study treatment; or 2) was present prior to study treatment, but worsened during study treatment. This would include any condition resulting from concomitant illnesses, reactions to concomitant medications, or progression of disease states. Pregnancy should be documented as an adverse event and should be reported to the clinical monitor and to the Sponsor immediately upon learning of the event

Serious Adverse Event (SAE) – An SAE is any untoward medical occurrence that:

- Results in death
- Is life threatening
- Requires in-patient hospitalization or prolongation of existing hospitalization
- Results in persistent or significant disability/incapacity (i.e., a significant persistent or permanent change, impairment, damage, or disruption to the subject's body)
- Is a congenital anomaly/birth defect, or
- Requires intervention to prevent permanent damage (the use of the investigational product resulting in a condition which requires medical or surgical intervention to preclude permanent impairment of the body structure or a body function). Important medical events that may not result in death, be life-threatening, or require hospitalization may be considered an SAE when, based upon appropriate medical judgment, they may jeopardize the patient or subject and may require medical or surgical intervention to prevent one of the outcomes listed in the above definition.

Diagnoses and conditions that are considered Serious Adverse Events include:

- Microbial Keratitis (MK)
- Iritis
- Permanent decrease in best spectacle corrected visual acuity equivalent to 2 acuity lines or greater
- Central Corneal Opacity
- Central Corneal Neovascularization
- Uveitis
- Endophthalmitis
- Hypopyon
- Hyphemia
- Penetration of Bowman's Membrane
- Persistent Epithelial Defect
- Limbal cell Damage leading to Conjunctivalization

Significant Adverse Events – Those events that are usually symptomatic and warrant discontinuation (temporary or permanent) of the test article (excluding Serious Adverse Events). Diagnoses and conditions that are considered Significant Adverse Events include the following:

- Contact Lens Induced Peripheral Ulcer (CLPU)
- Significant Infiltrative Events (SIE)
- Superior Epithelial Arcuate Lesions (SEALs)
- Any Temporary Loss of > 2 Lines of BSCVA
- Other grade 3 or higher corneal findings, such as abrasions or edema
- Any corneal event which necessitates temporary lens discontinuation > 2 weeks
- Non-contact lens related corneal events - e.g. EKC (Epidemic Keratoconjunctivitis)
- Asymptomatic Corneal Scar

Non-Significant Adverse Events – Those conditions that are usually asymptomatic and usually do not warrant discontinuation (temporary or permanent) of the test article. However, the Investigator may choose to treat as a precautionary measure. Diagnoses and conditions that are considered Non-Significant Adverse Events include the following:

- Non-significant Infiltrative Event
- Contact Lens Papillary Conjunctivitis
- Superficial Punctate Keratitis
- Conjunctivitis: Bacterial, Viral, Allergic
- Blepharitis
- Meibomianitis
- Contact Dermatitis
- Localized Allergic Reactions
- Any corneal event not explicitly defined as serious or significant adverse event, which necessitates temporary lens discontinuation < 2 weeks

Adverse Device Effect (ADE) – A sub-set of AEs, and include only those adverse events that are cause by or related to the investigational device or study procedure.

Unanticipated Adverse Device Effect (UADE) – Any serious adverse effect on health or safety or any life-threatening problem or death caused by, or associated with, the test article, if that effect, problem, or death was not previously identified in nature, severity, or degree of incidence in the investigational plan, investigator’s brochure or protocol, or any other unanticipated serious problem associated with the test article that relates to the rights, safety and welfare of subjects.

Causality Assessment – A determination of the relationship between an adverse event and the test article. The test article relationship for each adverse event should be determined by the investigator using these explanations:

- Not Related- An adverse event that is not related to the use of the test article.
- Doubtful – An adverse event for which an alternative explanation is more likely, e.g. concomitant treatment, concomitant disease(s), or the relationship of time suggests that a causal relationship is not likely.
- Possible – An adverse event that might be due to the use of the test article. An alternative explanation, e.g. concomitant treatment, concomitant disease(s), is inconclusive. The relationship in time is reasonable. Therefore, the causal relationship cannot be excluded.
- Probable – An adverse event that might be due to the use of the test article. The relationship in time is suggestive (e.g. confirmed by de-challenge). An alternative explanation is less likely, e.g. concomitant treatment or concomitant disease(s).
- Very Likely – An adverse event that is listed as a possible adverse effect (device) or adverse reaction (drug) and cannot be reasonably explained by an alternative explanation, e.g. concomitant treatment of concomitant disease(s). The relationship in time is very suggestive, e.g. it is confirmed by de-challenge and re-challenge.

Severity Assessment – A qualitative assessment of the degree of intensity of an adverse event as determined by the investigator or reported to him/her by the subject. The assessment of severity is made irrespective of test article relationship or seriousness of the event and should be evaluated according to the following scale:

- Mild – Event is noticeable to the subject, but is easily tolerated and does not interfere with the subject’s daily activities.
- Moderate – Event is bothersome, possibly requiring additional therapy, and may interfere with the subject’s daily activities.
- Severe – Event is intolerable, necessitates additional therapy or alteration of therapy and interferes with the subject’s daily activities.

